## 5 STOMATITIS AND MUCOSITIS

Preventive measures may include a comprehensive oral examination to identify and treat any potential risk for complications before study treatment is initiated. Appropriate correction of local factors should be instituted as indicated, such as modification of ill-fitting dentures and appropriate care of gingivitis. During treatment with cabozantinib, good oral hygiene and standard local treatments such as non-traumatic and non-irritating cleansing, and oral rinses

(e.g. with a weak solution of salt and baking soda) should be maintained. Lips should be kept moisturised with lip balm. The use of lipstick, lip-gloss, and vaseline should be avoided.

Local treatment should be instituted at the earliest onset of symptoms. Obtain bacterial/viral culture if oral infection is suspected and treat infection as clinically indicated.

## **6 SKIN AND SUBCUTANEOUS TISSUE DISORDERS**

### Wound healing and surgery

Cabozantinib has the potential to cause wound healing complications and wound dehiscence which may even occur long after a wound has been considered healed. Therefore, surgical and traumatic wounds must not only be completely healed prior to starting cabozantinib treatment but must also be monitored for wound dehiscence, wound infection and other signs of impaired wound healing while the subject is being treated with cabozantinib. If dehiscence occurs, cabozantinib treatment should not be restarted until complete healing has taken place.

Treatment with cabozantinib should be stopped at least 28 days prior to scheduled surgery. The decision to resume treatment with cabozantinib after surgery should be based on clinical judgment of adequate wound healing.

### Palmar-plantar erythrodysesthesia syndrome

Palmar-plantar erythrodysesthesia syndrome (also known as hand-foot syndrome), skin rash (including blister, erythematous rash, macular rash, skin exfoliation, dermatitis acneiform, and papular rash), pruritus, dry skin, erythema, pigmentary changes, and alopecia have been reported with cabozantinib. All subjects on study should be advised on prophylactic measures including the use of emollients, removal of calluses, avoidance of exposure of hands and feet to hot water leading to vasodilatation, protection of pressure-sensitive areas of hands and feet and use of cotton gloves and socks to prevent injury and keep the palms and soles dry.

Early manifestations include tingling, numbness, mild hyperkeratosis, and symmetrical red and swollen areas on the palms and soles. The lateral sides of the fingers or periungual zones may also be affected. Adequate interventions are required to prevent worsening of skin symptoms such as blisters, desquamations, ulcerations, or necrosis of affected areas. Analgesics may be required for pain control.

Aggressive management of symptoms is recommended, including early dermatology referral. Treatment recommendations in response to PPES are summarised in [Table A1. 3](#).

**Table A1. 3 Dose Modification Criteria and Recommended Guidelines for Treatment-emergent Hand-Foot Syndrome (PPES)**

Common Terminology Criteria for Adverse Events (CTCAE) version 5.0 Grade	Action to Be Taken
Grade 1	Study treatment may be continued at the current dose if PPES is clinically insignificant and tolerable. Otherwise, study treatment should be reduced to the next lower dose level. a Start urea 20% cream twice daily (b.i.d.) AND clobetasol 0.05% cream once daily (q.d.). Reassess at least weekly; if PPES worsens at any time or does not improve after 2 weeks, proceed to the intervention guidelines for Grade 2.
Grade 2	Study treatment may be continued if PPES is tolerated. Study treatment should be dose reduced or interrupted if PPES is intolerable. Continue urea 20% cream b.i.d. AND high potency steroid cream (e.g. clobetasol 0.05%) q.d. and add analgesics (e.g. NSAIDs/gamma-aminobutyric acid agonists) for pain control if needed. Reassess at least weekly; if PPES worsens or affects self-care, proceed to the intervention guidelines for Grade 3.
Grade 3	Interrupt study treatment until severity decreases to Grade 1 or 0. Continue treatment of skin reaction with high potency steroid cream (e.g. clobetasol 0.05%) b.i.d. AND analgesics. Resume study drug at a reduced dose if PPES recovers to Grade $\leq$ 1. Discontinue subject from study treatment if PPES does not improve within 6 weeks.

NSAID = Non-steroidal anti-inflammatory drug; PPES = Palmar-plantar erythrodysesthesia syndrome.

a Permitted dose levels are defined by individual protocols.

## 7 ANGIOEDEMA

Angioedema should be managed according to standard practice. The subject should be observed until symptoms resolve, with particular attention to maintaining an open airway.

## 8 OSTEONECROSIS

Osteonecrosis has been reported in subjects treated with cabozantinib. Additional risk factors include use of bisphosphonates and denosumab, chemotherapy and anti-angiogenic drugs, use of corticosteroids, local radiotherapy, and dental or orofacial surgery procedures.

Osteonecrosis of the jaw (ONJ) can manifest as jaw pain, osteomyelitis, osteitis, bone erosion, tooth or periodontal infection, toothache, gingival ulceration, or gingival erosion. Persistent pain or slow healing of the mouth or jaw after dental surgery may also be manifestations of ONJ.

Perform an oral examination prior to initiation of cabozantinib and periodically during cabozantinib therapy. Advise subjects regarding oral hygiene practice and to quickly report symptoms to the Investigator. Caution should be used in subjects receiving bisphosphonates.

Invasive dental procedures should be avoided. In cases where dental procedures are unavoidable, treatment with cabozantinib should be held for at least 4 weeks prior to the procedure and resumed after complete wound healing has occurred. Bone healing may often require a protracted time.

If ONJ occurs, cabozantinib treatment should be held and should not be restarted until the condition has sufficiently healed and the Sponsor has approved the re-initiation of therapy.

## 9 PROTEINURIA

Proteinuria has been reported with cabozantinib. Proteinuria should be monitored by measuring urine protein/creatinine ratio (UPCR). [Table A1.4](#) provides treatment guidelines for proteinuria deemed related to cabozantinib.

Cabozantinib should be discontinued in subjects who develop nephrotic syndrome (proteinuria  $>3.5$  g per day in combination with low blood protein levels, high cholesterol levels, high triglyceride levels, and oedema).

**Table A1.4 Management of Proteinuria Related to Cabozantinib**

Severity of Proteinuria (UPCR)	Management of Proteinuria
$\leq 1$ mg/mg ( $\leq 113.1$ mg/mmol)	
 
No change in cabozantinib treatment or monitoring
 

$>1$ and $<3.5$ mg/mg ( $>113.1$ and $<395.9$ mg/mmol)	
 
Consider confirming with a 24-hour protein assessment within 7 days
 
No change in cabozantinib treatment required if UPCR <math>\leq 2</math> mg/mg or urine protein <math>\leq 2</math> g/24 hours on 24-hour urine collection.
 
Dose reduce or interrupt cabozantinib treatment if UPCR <math>>2</math> mg/mg on repeat UPCR testing or urine protein <math>>2</math> g/24 hours on 24-hour urine collection. Continue cabozantinib on a reduced dose if UPCR decreases to <math><2</math> mg/mg. Consider holding cabozantinib treatment if UPCR remains <math>>2</math> mg/mg despite a dose reduction until UPCR decreases to <math><2</math> mg/mg. Restart cabozantinib treatment at a reduced dose after a dose hold unless otherwise approved by sponsor.
 
Repeat UPCR within 7 days and once per week. If UPCR <math><1</math> mg/mg on 2 consecutive readings, UPCR monitoring can revert to protocol-specific times. (Second reading is confirmatory and can be done within 1 week of first reading.) If UPCR remains <math>>1</math> mg/mg and <math><2</math> mg/mg for 1 month or is determined to be stable (<math><20\%</math> change) for 1 month, check urine protein/creatinine per protocol or as clinically indicated.
 

$\geq 3.5$ mg/mg ( $\geq 395.9$ mg/mmol)	
 
Hold cabozantinib treatment pending repeat UPCR within 7 days and/or 24-hour urine protein.
 
If <math>\geq 3.5</math> mg/mg on repeat UPCR, continue to hold cabozantinib treatment and check UPCR every 7 days. If UPCR decreases to <math><2</math> mg/mg, restart cabozantinib treatment at a reduced dose and monitoring of urine protein/creatinine should continue weekly until the UPCR decreases to <math><1</math> mg/mg. If UPCR remains <math>>1</math> mg/mg and <math><2</math> mg/mg for 1 month or is determined to be stable (<math><20\%</math> change) for 1 month, check urine protein/creatinine per protocol or as clinically indicated.
 

Nephrotic syndrome	
 
Discontinue all study treatment
 

UPCR = Urine protein/creatinine ratio.

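### Protocol Table A1.4, row for UPCR above 1 and below 3.5 mg/mg: the no-change and the reduce-or-interrupt bullets both apply to certain discordant UPCR and 24-hour results, and nothing says which prevails.

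*Protocol*

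**What the plan says.** Protocol Appendix 4, section 9 (Proteinuria) names UPCR as the monitoring measure and refers to Table A1.4 for management. Four bullets in the table's middle row (UPCR above 1 and below 3.5 mg/mg) matter here.

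- The first makes a 24-hour collection optional: "Consider confirming with a 24-hour protein assessment within 7 days".
- The second is permissive. It opens "No change in cabozantinib treatment required if UPCR" and is met by a UPCR of at most 2 mg/mg or a 24-hour protein of at most 2 g.
- The third is directive. It opens "Dose reduce or interrupt cabozantinib treatment if UPCR", sets the UPCR threshold at above 2, and continues "mg/mg on repeat UPCR testing or urine protein", with the 24-hour threshold at above 2 g. Its UPCR limb therefore counts only on a repeat test.
- The fourth calls for the repeat: "Repeat UPCR within 7 days and once per week".

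Table 4 sends specific conditions to Section 6.2.4, which sends the reader to Appendix 4. Table A1.4 is therefore the operative rule for proteinuria, and the general grade-based table does not override it.

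**The concern.** Two rules meant to divide patients into two groups should be complements. The complement of a condition of the form A or B is not-A and not-B. Here both rules use an or, so they overlap whenever one test satisfies the first rule and the other test satisfies the second.

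A site that relies on the permissive bullet could then leave unchanged a dose that the next bullet says to reduce or interrupt. Another of the approximately 50 sites, holding the same two results, could act on the directive bullet. That is a patient-safety matter first.

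It also reaches the data. Under Protocol Section 8.1.2.4, a laboratory abnormality becomes reportable as an AE if, among other triggers, it changes how the study drug is given. The bullet that a site follows can therefore affect whether the proteinuria is recorded as an AE. It can also affect the SAP Section 3.2.2.1 tables of TEAEs associated with interruption and dose reduction, and the average daily dose in SAP Appendix 1, item 21.

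**Working it through.** The plan states no figure to reproduce, and no power or sample-size arithmetic applies. The check is a truth table on the two bullets.

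**Inputs (all from Table A1.4, middle row).** U is the latest UPCR in mg/mg, R is a repeat UPCR if done, and H is the 24-hour protein in g if done.

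- No change required: U ≤ 2 or H ≤ 2.
- Reduce or interrupt: R > 2 or H > 2.

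Taking the latest UPCR for the first rule is a reading, since the table does not say which value counts.

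**Two worked cases.**

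- UPCR 1.7, H = 2.3. No change: 1.7 ≤ 2, met. Reduce or interrupt: 2.3 > 2, met. Both apply.
- Repeat UPCR 2.4, H = 1.8. No change: 1.8 ≤ 2, met. Reduce or interrupt: 2.4 > 2, met. Both apply.

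**Full enumeration.** The first UPCR has 2 states, the repeat has 3 (not done, ≤ 2, > 2) and H has 3, so there are 2 × 3 × 3 = 18 combinations. In 6 of them the latest UPCR and H fall on opposite sides of 2:

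| First UPCR | Repeat UPCR | 24-hour protein | No change | Reduce or interrupt |
|---|---|---|---|---|
| ≤ 2 | not done | > 2 g | yes | yes |
| ≤ 2 | ≤ 2 | > 2 g | yes | yes |
| > 2 | ≤ 2 | > 2 g | yes | yes |
| ≤ 2 | > 2 | ≤ 2 g | yes | yes |
| > 2 | > 2 | ≤ 2 g | yes | yes |
| > 2 | not done | ≤ 2 g | yes | no |

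Both bullets apply in 5 of these 6. The sixth escapes because the UPCR limb of the directive bullet needs a repeat test. In the other 12 combinations the tests agree or no 24-hour result exists, and the bullets never both apply. In one of those 12 (a first UPCR above 2 with neither a repeat nor a 24-hour result) neither bullet applies yet.

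**Search for a tie-break.**

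- Section 9 of the appendix makes UPCR the monitoring measure, while the row describes the 24-hour test as confirming. These point in different directions, and neither says that one overrides the other.
- Inclusion criterion 8(g) and footnote g of Table 2 also offer the two tests as alternatives without ranking them.
- The later steps of the directive bullet are written in UPCR alone: they continue the reduced dose once UPCR is below 2. A patient who entered that bullet through 2.3 g with a UPCR of 1.7 already satisfies this condition, so the row does not work through the discordant case.

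**The case against.** The strongest reply is that the overlap is narrow and the table is guidance. Much of that stands.

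- A reader might infer that the bullets collide whenever the two tests fall on opposite sides of 2. They do not. The repeat-test qualifier removes one of the six discordant combinations.
- A reader might call the two instructions opposite. The first says only that no change is required; it does not forbid one. A site that reduces or interrupts breaches neither bullet. The difficulty runs one way: a site may rely on the permissive bullet when the directive one is also met.
- A reader might think the collision likely, because the repeat UPCR and the 24-hour collection share a 7-day window. The 24-hour test is only to be considered, and Table 5 leaves urine chemistry to the investigator's judgement. The documents support saying that both results can be on file, and no more.
- Section 6.2.2 already lets investigators interrupt for AEs at any time and modify the dose below the Table 4 thresholds. The directive bullet itself offers two actions. Dosing would therefore vary between sites even with clean wording.
- The affected outputs are descriptive safety summaries in a study with no comparator arm, and Protocol Section 11.3 excludes testing of safety endpoints. No effect on the primary ORR test is shown.

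What does not stand is the idea that discretion settles the matter. Section 6.2.2 gives latitude to modify earlier than the thresholds. It does not say that a stated instruction to reduce or interrupt may be set aside because a neighbouring bullet is also met.

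**Conclusion.** The point holds as a wording conflict inside one row of Table A1.4. Both bullets apply when UPCR is at most 2 mg/mg with 24-hour protein above 2 g, and when repeat UPCR is above 2 mg/mg with 24-hour protein at most 2 g. It rests on reading both connectors literally, on using the latest UPCR for the no-change limb, and on the optional 24-hour collection having been done.

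The 5 of 6 counts logical combinations, not patients. The documents give neither a UPCR distribution nor a rate of 24-hour testing, so the frequency cannot be derived. A reader might try to size the overlap by setting 24-hour protein equal to UPCR times daily creatinine excretion C, which puts it between UPCR 2 and 2/C. Assuming C from 0.7 to 1.8 g/day:

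- C = 0.7: 2/0.7 = 2.86, and (2.86 − 2)/2.5 = 34% of the row's width.
- C = 1.5: 2/1.5 = 1.33, and (2 − 1.33)/2.5 = 27%.
- C = 1.8: 2/1.8 = 1.11, and (2 − 1.11)/2.5 = 36%.

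The documents do not support using these as the size of the problem. The excretion values are assumed, the percentages are shares of a numeric interval and not of patients, and the band above 2 also needs the repeat test. The point stands without them.

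The table should be corrected because the conflict is between two stated dosing rules and bears on patient safety.

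**What to change.** Reword the second and third bullets of the middle row so that exactly one applies to any pair of UPCR and 24-hour results, and state how the two tests combine, or which governs, when they disagree around 2. State also which UPCR value (first or repeat) each bullet refers to. More than one wording would remove the overlap, and they lead to different dosing, so the choice belongs to the clinical team. No rule is proposed here.

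The cost is about one sentence in Appendix 4, with no extra test or visit. If dosing is already complete, the sponsor should document how discordant results were handled, so that the interruption, dose-reduction and AE tables can be read with that in mind.

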## 10 NERVOUS SYSTEM DISORDERS

Cabozantinib appears to represent minimal risk of adverse neurological effects based on nonclinical Good Laboratory Practice (GLP)-compliant toxicology studies. Dysphonia, dysgeusia, headache, dizziness, confusional state, convulsion, depression, memory impairment, hypoesthesia, peripheral neuropathy, insomnia and ataxia have been observed in clinical studies with cabozantinib. In addition, hepatic encephalopathy has been observed in HCC clinical studies with cabozantinib. The development of any new or progressive, unexplained neurological symptoms should be assessed for underlying causes.

RPLS has been reported and should be considered in any subject presenting with seizures, headache, visual disturbances, confusion or altered mental function. Cabozantinib treatment should be discontinued in subjects with RPLS.

## 11 HEPATIC EVENTS

Investigators should monitor for Drug induced liver injury (DILI) diligently and report any potential events.

Elevation of aminotransferases (ALT and AST): Evaluation of subjects with elevated transaminases or bilirubin should be individualized and guided by the presence of specific risk factors such as liver conditions (e.g. liver cirrhosis, thrombosis of portal or hepatic vein, HCC, hepatitis), concomitant hepatotoxic medication, alcohol consumption, and cancer related causes.

If not otherwise specified in individual protocols, cabozantinib should be interrupted for related CTCAE Grade 3 or higher hepatic injury (transaminase increase to  $> 5 \times$  ULN) and when transaminase increases are accompanied by progressive elevations of total bilirubin, and/or elevations of coagulation tests (e.g. International Normalized Ratio [INR]). More frequent monitoring of transaminases should be considered and cabozantinib should be held until the aetiology of the abnormalities is determined and these abnormalities are corrected or stabilize at clinically acceptable levels. Cabozantinib should be discontinued if hepatic dysfunction is not reversed despite interruption of study treatment. Elevations of aminotransferases when hepatic metastases are present may not require dose modifications if there are no progressive changes in the aminotransferases (less than a doubling) and if there are no progressive elevations in serum bilirubin concentration or coagulation factors. Elevations  $> 3 \times$  ULN of ALT or AST concurrent with  $> 2 \times$  ULN total bilirubin without other explanation (such as initial findings of cholestasis and obstructive disease, viral hepatitis, pre-existing or acute liver disease, or another drug capable of causing the observed injury) can indicate DILI. Study drug should be permanently discontinued in cases determined to be DILI according to Hy's Law review.

## 12 INFECTIONS AND INFESTATIONS

Infections are commonly observed in cancer subjects. Predisposing risk factor include a decreased immune status (e.g. after myelosuppressive anti-cancer therapies, splenectomy), destructive growth of the underlying malignancy including bone marrow infiltration with suppression of normal haematopoiesis, as well as the presence of intravenous (IV) devices.

Infections and abscesses should be treated with appropriate local care and systemic therapy. Cabozantinib should be held until adequate healing has taken place.

## 13 BLOOD AND LYMPHATIC SYSTEM DISORDERS

Haematological toxicities (i.e. neutropenia and thrombocytopenia) and associated complications have been observed after administration of cabozantinib and may be managed

with dose interruptions and/or dose reductions. Subjects with hematologic toxicities may require additional or more frequent laboratory tests according to institutional guidelines.

Dose reductions or dose interruptions for haematological toxicities are not mandated but can be applied as clinically indicated. Supportive care for thrombocytopenia or anaemia, such as transfusions, may be managed according to institutional guidelines. The use of colony-stimulating growth factors should be considered unless prohibited by a specific protocol. Febrile neutropenia or evidence of infection associated with neutropenia must be assessed immediately and treated appropriately and in a timely manner according to institutional guidelines.

#### **14        FATIGUE**

Common causes of fatigue, such as anaemia, deconditioning, emotional distress (depression and/or anxiety), poor nutrition, dehydration, sleep disturbance, and hypothyroidism should be ruled out and treated according to standard of care. Pharmacological management should be considered after disease specific morbidities have been excluded when not prohibited by a particular protocol.

#### **15        WEIGHT LOSS**

Anorexia and weight loss should be managed according to local standard of care including nutritional support. Pharmacologic therapy should be considered for appetite enhancement when not prohibited by a particular protocol.

#### **16        CORRECTED QT PROLONGATION**

The effect of orally administered cabozantinib 140 mg q.d. on QTc interval was evaluated in a placebo-controlled study in subjects with MTC. A mean increase of 10-15 ms in QTcF was observed after 4 weeks after initiating cabozantinib treatment. A concentration-QTc relationship could not be definitively established. Changes in cardiac wave form morphology or new rhythms were not observed. There were no events of torsades de pointes reported.

Unless otherwise specified in certain protocols, only subjects with a baseline QTcF  $\leq$ 500 msec are eligible for cabozantinib research studies. Cabozantinib should be used with caution in subjects with QT prolongation risk, a history of QT interval prolongation, or who are taking antiarrhythmics or other drugs known to prolong the QT interval. Concomitant treatment with strong CYP3A4 inhibitors, which may increase cabozantinib plasma concentrations, should be avoided.

If at any time on study there is an increase in QTcF to an absolute value  $>$ 500 ms or an increase of  $>$ 60 ms above baseline, two additional 12-lead ECGs must be performed with intervals not less than 3 minutes apart within 30 minutes after the initial ECG.

If the average QTcF from the three ECGs is  $>$ 500 ms or increased by  $>$ 60 ms above baseline, the following actions must be taken:

- Withhold study treatment;
- Immediately notify the Sponsor;
- Hospitalise symptomatic subjects (e.g. with palpitations, dizziness, syncope, orthostatic hypotension, a significant ventricular arrhythmia on ECG) for a thorough cardiology evaluation and management;

- Consider cardiology consultation for asymptomatic subjects for evaluation and management;
- Check electrolytes, especially magnesium, potassium and calcium; correct abnormalities as clinically indicated;
- Check concomitant medications for any medication that may have contributed to QT prolongation, and if possible, discontinue these medications (<http://www.qtdrugs.org>);
- Repeat ECG triplicates hourly until the average QTcF is  $\leq 500$  msec, or otherwise determined by consultation with a cardiologist or appropriate expert.

Subjects with QTc prolongation and symptoms must be monitored closely until the QTc elevation and symptoms have resolved. Study treatment may be restarted at a reduced dose level if all of the following conditions are met:

- Symptoms are determined to be unrelated to the QT interval prolongation;
- The QTcF value  $>500$  ms or increase of  $>60$  ms above baseline is not confirmed according to protocol procedures;
- Study treatment has been interrupted through a minimum of 1 week following the return of the QTcF to  $\leq 500$  msec or return to  $\leq 60$  ms above baseline;
- QT prolongation can be unequivocally associated with an event other than cabozantinib administration and is treatable/has been resolved;

Sponsor has reviewed all available information and has agreed to the continuation of study treatment.

Following reinitiation of study treatment, ECGs must be repeated weekly for 2 weeks, then every 2 weeks for 1 month, then according to the protocol-defined time points.

All study treatment must be permanently discontinued if either of the following applies:

- Cardiac evaluation confirms that symptoms are the consequence of QT interval prolongation;
- Recurrence of QTcF prolongation (confirmed by central ECG lab) after reinitiation of study treatment at a reduced dose.
- 

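### The QTc restart rule can start its one-week count while a hold criterion is still met, because recovery is written with *or* where *and* is needed

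*Protocol*

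**What the plan says.** All of the rule is in Protocol Appendix 4, section 16 (Corrected QT prolongation).

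- **Hold.** A QTcF above 500 ms, or more than 60 ms above baseline, at any time on study calls for two further ECGs. "If the average QTcF from the three ECGs is" above 500 ms or up by more than 60 ms, treatment is withheld and the Sponsor is told at once.
- **Repeat ECGs.** "Repeat ECG triplicates hourly until the average QTcF is" 500 ms or less, or as a cardiologist or other expert determines. The 60 ms limit is not mentioned here.
- **Restart.** "Study treatment may be restarted at a reduced dose level if all of the following conditions are met". The conditions are: symptoms unrelated to the QT finding; a value over 500 ms or an increase of more than 60 ms "above baseline is not confirmed according to protocol procedures"; a one-week condition, namely that "Study treatment has been interrupted through a minimum of 1 week following the return of the QTcF to" a level of 500 ms or less, or to 60 ms or less above baseline; a cause condition, namely that "QT prolongation can be unequivocally associated with an event other than cabozantinib administration and is treatable/has been resolved"; and a Sponsor condition, namely that "Sponsor has reviewed all available information and has agreed to the continuation of study treatment".
- **After restart.** "Following reinitiation of study treatment, ECGs must be repeated weekly for 2 weeks", and then at longer intervals.

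The note to Table 4 (Protocol Section 6.2.2) sends condition-specific criteria to Section 6.2.4, which leads to Appendix 4. The same note sends reinstatement after an interruption to Section 6.2.3, which asks for Grade 1 or less, or a return to baseline.

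**The concern.** A hold triggered by either of two limits is over only when neither limit is exceeded. The opposite of an *or* trigger is an *and* recovery. The one-week condition keeps the *or*, so the count can begin when one limit has cleared and the other has not.

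At stake is the meaning of the week. It reads as a drug-free observation period after QTcF has recovered. If it starts early, some of it is spent with QTcF at a level that would itself require a hold, and less than a full week of recovered QTcF is assured before restart is considered. Two sites could also date the same recovery differently. This is a subject-safety rule. It has no bearing on the ORR test.

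**Working it through.** There is no figure in the plan to reproduce, so the check is one of logic.

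**Inputs.** The limits of 500 ms and +60 ms and the two *or* connectors come from Appendix 4, section 16. The baselines are illustrations. Exclusion criterion 9 bars only QTcF above 500 ms, so they are eligible values.

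**Rules.** Let B be baseline QTcF and Q the current triplicate average, in ms.

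- Hold: Q > 500 or Q − B > 60.
- Clock start as written: Q ≤ 500 or Q − B ≤ 60.
- Clock start with *and*: Q ≤ 500 and Q − B ≤ 60, that is, Q ≤ min(500, B + 60).

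**Overlap of hold and written clock.** Both are true exactly when one limit is exceeded and the other is not, so Q lies between B + 60 and 500. The width is |500 − (B + 60)| = |440 − B| ms.

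| B | Q values meeting both (whole ms) | Width |
|---|---|---|
| 410 | 471–500 | 30 |
| 430 | 491–500 | 10 |
| 440 | none | 0 |
| 460 | 501–520 | 20 |
| 480 | 501–540 | 40 |

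**Subjects who broke both limits.**

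- B = 430. At 510, 510 − 430 = +80, so both limits are broken. At 498, 498 − 430 = +68: the 500 ms limit has cleared and the written clock can start, but +68 still meets the hold criterion. With *and*, the clock starts at 490 or below.
- B = 460. At 530, 530 − 460 = +70, so both limits are broken. At 515, 515 − 460 = +55: the 60 ms limit has cleared and the written clock can start, but 515 is still above 500. With *and*, the clock starts at 500 or below.

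**Subjects who broke one limit.** With B = 410 and Q = 480 (+70), the 500 ms limit was never broken. If *return* means recovery of the limit that was broken, the clock waits for 470 and is right. Only if the wording is detached from the broken limit is the clock satisfied at the triggering ECG.

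**Hourly triplicates.** The stop at Q ≤ 500 can be met while the hold criterion is still met when B < 440 (B = 430: 491–500). For B ≥ 440, B + 60 is at least 500, so reaching 500 clears both limits.

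**After the change.** The *and* form is the exact negation of the hold, so the overlap is empty. A check of whole-ms baselines from 380 to 500 found none.

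**The case against.** A reader might infer that subjects can be put back on cabozantinib while still in the hold range. The documents do not establish that, for four reasons.

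1. Section 6.2.3 governs reinstatement and asks for Grade 1 or less, or baseline. An increase of 68 ms is not baseline. Whether it is Grade 1 depends on CTCAE cut-offs that the documents do not reproduce. Section 16 might be argued to override 6.2.3 as the more specific text, but nothing says so.
2. The non-confirmation condition, read as QTcF status when restart is considered, negates the hold trigger. That requires 500 ms or less and 60 ms or less above baseline, so it would bar restart at 498 (+68) or at 515.
3. The hold rule applies at any time on study, so dosing on a known average of +68 would contradict it.
4. The Sponsor must review the case and agree.

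Two further points are fair. A sympathetic reader can take *return* to mean that every limit broken must recover, which would give the right answer for both-limit subjects too. And breaking both limits is demanding: at a baseline of 430 it needs a rise of more than 70 ms (500 − 430), and at 410 more than 90 ms. Section 16 itself reports a mean rise of 10–15 ms at 140 mg daily, against 60 mg here.

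These points remove the claim of unsafe restart and make the situation look rare. They do not repair the clock. None of the four gates says when the week begins, and the sympathetic reading has to be supplied by the reader.

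**Conclusion.** The point holds as a minor defect in a safety rule. Read literally, the one-week count can begin before full recovery in a subject who exceeded both limits, so part of the post-recovery week may precede recovery. The range of QTcF in which this can happen is |440 − baseline| ms wide. That the overlap exists at almost every baseline describes the rule and says nothing about how many subjects meet it. The documents give no rate of QTc holds, so the number is unknown; it is probably small. ORR and power are unaffected.

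The conclusion rests on reading *or* as written. If every broken limit is taken to need recovery, the intent is right and only the wording is loose.

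A reader might also infer that the non-confirmation condition makes restart impossible for everyone, since a hold already rests on a triplicate average, and that it should therefore go. The documents do not support that either. They name no confirmation procedure and do not call the triplicate a confirmation. Later repeats or a central reading may have been meant, although a central laboratory is named only for recurrence and Protocol Section 8.5 provides a local reader. The missing detail errs on the side of keeping the drug off, and removing the condition would take away a possible safeguard.

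**What to change.** In Protocol Appendix 4, section 16:

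- Start the one-week clock only when the average QTcF is 500 ms or less **and** no more than 60 ms above baseline.
- Use the same joint criterion to stop the hourly triplicates, keeping the option for a cardiologist or other expert to decide.
- Leave the non-confirmation condition in the list of requirements that must all be met. If it is edited, only clarify it: a repeat triplicate average at the time of restart is 500 ms or less and no more than 60 ms above baseline.
- Leave the symptom, other-cause and Sponsor-agreement conditions as they are.

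The cost is a wording change in a protocol amendment. It may count as substantial under Protocol Section 13.1.1 because it concerns subject safety, and it can be combined with other changes. Some subjects may have a longer hold or a few more repeat ECGs. The analysis plan does not change.
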